8.4 Duration of Treatment

14 days

(Dosage and administration of continuous intravenous infusion: 72 hours, approved dosage and administration: 14 days)

In principle, this drug should be administered for 14 days. However, after administration for 7 days after the start of administration and completion of NIHSS evaluation, administration of investigational product may be completed only when neurological symptoms due to the primary disease have resolved to the pre-onset state and stabilized, and when continuation of administration of investigational product is not clinically significant and the investigator (subinvestigator) judges that administration of Midi-chlorian can only result in disadvantages such as restraint of the subject.

[Rationale]

Duration of administration of continuous intravenous infusion dosage and administration: It is said that the infarct foci are completed in about 1 day after cerebral infarction attack ⁶⁾, it is also reported that the penumbra remains for about 2 days and leads to infarction later ^{7,8)}, and that the plasma concentration of oxidized LDL, an oxidation marker, is high for 3 days after the onset ⁹⁾. The administration period was set at 3 days because it was considered that a sufficient blood concentration could be maintained at an early stage of 3 days after the onset until the infarct enlarged and completed, and higher efficacy could be obtained by scavenging radicals.

Duration of treatment with the approved dosage and administration: It was set to be 14 days based on the dosage and administration of RADICUT Injection 30 mg.

8.5 Concomitant medications and therapies

8.5.1 Prohibited Medications

Concomitant use of the following drugs is prohibited from the onset to the evaluation day 3 months after the onset.

- (1) Thrombolytics (rt-PA preparations, urokinase, etc.)
- (2) Addition of edaravone formulation
- (3) Any investigational product other than investigational product

[Rationale]

- (1) (2) This criterion was specified to possibly affect the efficacy evaluation.
- (3) These criteria were set because they may affect the evaluation of efficacy and safety.

8.5.2 Prohibited Concomitant Medications and Procedures

Concomitant use of the following therapies is prohibited from the onset to the evaluation day 3 months after the onset.

- (1) Surgical treatment for cerebral infarction (Bypass surgery, carotid endarterectomy)
- (2) Endovascular Treatment (Transarterial thrombolysis, angioplasty/thrombolysis using PTA balloon, intracranial stent placement, thrombus retrieval therapy, carotid artery stent placement)
- (3) Continuous transcranial Doppler (TCD), hypothermia, hyperbaric oxygen, and experimental therapies with unestablished efficacy

[Rationale]

This criterion was specified to possibly affect the efficacy evaluation.

8.5.3 Record concomitant medications and procedures

The investigator (subinvestigator) or a study collaborator will record the following contents of drugs and therapies used during the study period (from the onset to the evaluation day 3 months after onset) in the concomitant drugs and therapies section of the case report form. Saline, etc. for reconstitution of injections should not be recorded.

- (1) Concomitant medications: Name of drug, route of administration, duration of administration, reason for use, daily dose (drug used for the primary disease)
- (2) Concomitant therapies: name of therapy, duration of use, reason for use

8.6 Subject Management

(1) Lifestyle Guidance

The investigator (subinvestigator) or a study collaborator will give guidance to subjects with attention to the following points.

- 1) Subjects should be evaluated on the designated days. If the subject cannot visit the study site on the designated day, he/she must contact the investigator or study coordinator and follow his/her instructions.
- 2) Subjects should carry the study participation card with them and present it when they visit other hospitals or departments. Also, even if you are using drugs prescribed by your study doctor other than this study or drugs purchased at a pharmacy, you must tell the investigator (subinvestigator) or a collaborator. In addition, any new medication during the study must be reported to the investigator (subinvestigator) or study collaborator before use.
- 3) Subjects should notify the investigator or designee of any physical abnormalities.
- 4) The investigator (subinvestigator) or a study collaborator should instruct subjects to use reliable methods of contraception shown below from the day of informed consent to the next day after completion of administration of investigational product. Calendar, ovulation, symptothermal,

post-ovulation methods, and intravaginal methods are not acceptable methods of contraception.

Postmenopausal women who have been amenorrheic for at least 1 year or women who have undergone surgical hysterectomy or bilateral oophorectomy are excluded.

1) Not having sex

2) Performing two effective methods of contraception. A barrier contraceptive (Oral contraceptives, intrauterine ring, tubal ligation, vasectomy, etc.) plus a more effective contraceptive method is recommended.

(2) Guidance related to evaluation 3 months after onset

When the subject is discharged from the hospital, the investigator (subinvestigator) or a study collaborator will instruct the subject (Family members, caregivers, site staff, etc. as needed) to return to the hospital 3 months after the onset to undergo specified evaluations and tests.

In addition, the investigator (subinvestigator) or a study collaborator will instruct subjects (Family members, caregivers, site staff, etc. as needed) to record the subject's condition immediately before the visit day 3 months after the onset in the patient diary, regarding the following information necessary for the evaluation of functional independence of subjects 3 months after the onset.

- 1) Self-care, degree of independence during excretion, transfer, and transfer
- 2) Independence level of communication and social awareness

9. Examination/Observation

j) Only white blood cell count (WBC), red blood cell count (RBC), hemoglobin (Hb), hematocrit (Ht), platelets (Plt), AST (GOT), ALT (GPT), LDH, ALP, γ -GTP, total bilirubin (T-Bil), CK (CPK), urea nitrogen (BUN), serum creatinine (Cre), and eGFR will be examined urgently in the hospital to confirm the eligibility as a case.

k) Only red blood cell (RBC), platelet (Plt), AST (GOT), ALT (GPT), LDH, ALP, total bilirubin (T-Bil), CK (CPK), urea nitrogen (BUN), and serum creatinine (Cre) will be measured in the hospital every day for 5 days from the start day of treatment to confirm the safety of subjects.

9.2 Test/Observation Items and Timing

9.2.1 Items Related to Subject Demographics

The Investigator (or Subinvestigator) will investigate the following subject background factors before the start of treatment and record the details in the case report form. Even for items investigated after the onset but before obtaining informed consent, if the subject's consent to use the investigation results as pretreatment data in the study is obtained, the investigation results can be regarded as the investigation results at enrollment.

- (1) Gender
- (2) Date of birth (Western calendar)
- (3) Weight
- (4) Date and time of onset, date and time of visit, status at onset (Presence/absence of convulsion, clinical course, rationale for determination of cerebral infarction, etc.), disease type (Cardioembolic stroke, atherothrombotic cerebral infarction, lacunar infarction, other or indistinguishable)
- (5) Level of consciousness disturbed: Japan Coma Scale(JCS, 3-3-9 degree system)

0: Clear

I: Awake (confusion, delirium, senselessness)

1. The patient was mostly alert, but it was not clear at all.
2. Disorientation (Time, place, person).
3. I cannot tell my name or date of birth.

II: Awakens to stimulus *(stupor, lethargy, hypersomnia, somnolence, drowsiness)

10. Open the eyes easily with an ordinary voice.
20. Open the eyes by loud voice or shaking.
30. Repeated calls with painful stimuli barely open the eyes.

*Consciousness after awaking will not be considered.

III: Does not awaken when stimulated (Deepcoma, coma, semicomma)

100. Discharge pain stimuli
200. Slight movement of hands and feet or grimacing due to painful stimuli.
300. Does not respond at all to painful stimuli.

- (6) Medical history/complications
- (7) Confirmation of eligibility
- (8) Pre-symptomatic mRS(The subject or the subject's family will be interviewed.)

9.2.2 Administration status

The investigator (subinvestigator) or a study collaborator will confirm the administration status of investigational product and record the following items in the case report form.

- (1) Continuous IV infusion rate, start and stop dates and times
- (2) Date and time of starting administration of approved dosage and administration, and presence or absence of

completion of administration

(3) Stop date and time if treatment stopped

9.2.3 Items Related to Efficacy Evaluation

(1) NIHSS

NIHSS will be assessed before treatment, daily from Day1 (after the start of treatment) to Day7, on Day10, Day14, Week 3, at discharge, and 3 months later, and the date, time, and details of the assessment will be recorded in the case report form. The evaluator should be the investigator (subinvestigator) who has experience in evaluation in daily medical practice and has received a certain amount of training, and the same evaluator should evaluate each subject throughout the study period as much as possible.

(2) mRS

The Investigator (or Subinvestigator) will interview the subject according to the mRS Interview Form (Attachment 2) at 3 weeks, at discharge, and 3 months later, evaluate the mRS based on the assessment criteria form (Attachment 3), and record the date and contents of the evaluation in the case report form.

(3) BI

The investigator (subinvestigator) will assess BI on Day14, Week 3, at discharge, and 3 months later, and record the date and contents of the assessment in the case report form.

(4) FIM

FIM will be assessed 3 weeks later, at discharge, and 3 months later. The evaluator will be the investigator (subinvestigator) and study collaborator (occupational or physical therapist, etc.) who have received a certain amount of training, and the evaluation date and its contents will be recorded in the case report form.

(5) Period of starting rehabilitation

The Investigator (or Subinvestigator) must record in the CRF the date when the subject was released from bed and started rehabilitation.

(6) Duration of hospitalization

The investigator or subinvestigator will record the date of discharge, the place of discharge (Home, rehabilitation hospital, long-term care facility, etc.), and the reason for discharge in the case report form.

(7) Brain imaging

The investigator or the investigator's designee will obtain DWI, T2*WI, FLAIR, and MRA prior to dosing, DWI, T2*WI on Day4 (after completion of continuous IV infusion), DWI, T2*WI on Day14, and FLAIR 3

months later, and record the imaging dates in the CRF.

The infarct volume, degree of cerebral edema, and presence/absence and degree of intracranial hemorrhage will be evaluated by the Image Evaluation Committee.

[REDACTED]

[REDACTED]

[REDACTED]

9.2.4 Items Related to Safety Evaluation

9.2.4.1 Objective findings

(1) General laboratory tests: Hematology, serum chemistry, urinalysis

[Items to be measured from visit to before the start of administration]

The Investigator (or Subinvestigator) will perform emergency tests of the underlined items below in the hospital, confirm the eligibility as a subject, and record the date and time of blood sampling, date of confirmation of test results, and results of confirmation of test results (clinical significance) in the source documents. The date and time of blood sampling and test results will be recorded in the case report form.

In addition, all of the following tests will be measured at the contract laboratory testing institution, and the date of confirmation of the test results and the confirmation results (clinical significance) will be recorded. The test results provided by the contract laboratory testing institution will be retained by the study site and the sponsor.

The test items are as follows.

- Hematology: White blood cell count (WBC), Red blood cell count (RBC), Hematocrit (Ht), Hemoglobin (Hb), Platelets (Plt)
- Blood biochemistry: AST (GOT), ALT (GPT), LDH, ALP, γ -GTP, Total bilirubin (T-Bil), direct bilirubin (D-Bil), Total cholesterol (T-Cho), triglycerides (TG), total protein (TP), CK (CPK), Blood urea nitrogen (BUN), Serum creatinine (Cre), eGFR, Uric acid (UA), Na, K, Cl, albumin, glucose
- Urinalysis (qualitative): Sugar, protein, occult blood

[Items to be measured from the start of administration to the end of observation (3 months later)]

The Investigator (or Subinvestigator) must measure the underlined items below in the routine test in the hospital, confirm the test results, and record the date and time of blood sampling, date of confirmation of test results, and results of confirmation of test results (clinical significance) in the

source documents every day from Day1 (after the start of treatment) to Day5. The date and time of blood sampling and test results will be recorded in the case report form.

The investigator (subinvestigator) will measure all of the following tests at the contract laboratory testing institution on Day4 (before the end of continuous intravenous infusion), Day7, Day10, Day14, Week 3, and at discharge, and record the date of confirmation of test results and the results of confirmation (clinical significance). The test results provided by the contract laboratory testing institution will be retained by the study site and the sponsor.

The test items are as follows.

- Hematology: white blood cell count (WBC), red blood cell count (RBC), hematocrit (Ht),
Hemoglobin (Hb), Platelets (Plt)
- Blood biochemistry: AST (GOT), ALT (GPT), LDH, ALP, γ -GTP,
Total bilirubin (T-Bil), direct bilirubin (D-Bil),
Total cholesterol (T-Chol), triglycerides (TG), total protein (TP),
CK (CPK), Blood urea nitrogen (BUN), Serum creatinine (Cre), eGFR,
Uric acid (UA), Na, K, Cl, albumin, glucose
- Urinalysis (qualitative): Sugar, protein, occult blood

(2) Standard 12 lead ECG

The investigator (subinvestigator) will perform standard 12 lead ECG at baseline and Day4 (before completion of continuous intravenous infusion) to determine whether there are any abnormal findings. The date and time of standard 12 lead ECG, ECG parameters (Heart rate, PR interval, QRS interval, RR interval, QT interval, and QTc interval), and assessment results will be recorded in the CRF. Clinically significant abnormal findings, if determined by the investigator or subinvestigator, should be recorded as adverse events. The investigator will maintain ECG charts as source documents.

(3) Vital signs

The investigator/subinvestigator will measure systolic/diastolic blood pressure, pulse rate, and body temperature (Axillary, oral or tympanic body temperature) before administration, on Day4 (before the end of continuous intravenous infusion), Day7, and Day14, and record the date of measurement and the test results in the case report form. Blood pressure should be measured in the same arm throughout the study period whenever possible. Clinically significant abnormal findings, if determined by the investigator or subinvestigator, should be recorded as adverse events.

(4) Neurological Examination

The Investigator (or Subinvestigator) will perform a neurological examination on the healthy side once from the onset to Day5, and then on Day14, Week 3, at the time of discharge, and 3 months later. The tests that may be

affected by the subject's condition or treatment (Disturbance of consciousness, speech/articulation disorder, cognitive disorder, urinary catheter, etc.) will be performed on the day of observation, and the date and results will be recorded in the CRF.

NEUROLOGIC EXAMINATION (FUNCTIONAL)

- Sensory tests: Pain, sense of touch, sense of temperature, sense of vibration, sense of position
- Reflex function: Biceps brachii reflex, triceps brachii reflex, patellar tendon reflex, Achilles tendon reflex

Each item of the sensory test will be assessed according to the following criteria.

- 0: No abnormality
- 1: Weakening or disappearance in the fingers or toes
- 2: Weakness or disappearance up to the wrist or ankle
- 3: Decreased or disappeared up to the forearm or lower leg
- 4: Weakness or disappearance in the upper arm or thigh

Reflex function will be assessed according to the following criteria.

- 0: No abnormality or increased
- 1: Decreased
- 2: Elimination

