5.4.2 Safety Endpoints

- (1) Adverse Events and Adverse Drug Reactions
- (2) Neurological Examination
- (3) General laboratory tests
- (4) Vital signs
- (5) Standard 12 lead ECG

[Rationale]

Because delayed neurotoxicity was observed in nonclinical studies of this drug, in addition to general safety endpoints, a neurological examination was included to check for the development of symptoms due to neuropathy of peripheral nerves and notochord.

[figure not shown]
6. Target Sample Size and Study Duration

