11.2 Significant Adverse Events

For the purpose of examining the safety profile, AEs of special interest are defined as follows.

- (1) Renal disorder
Serum creatinine >2.0 mg/dL
- (2) Drug-induced liver injury
¹⁹ if all of the following definitions of Hy's law are met:
 - a) AST or ALT $> 3 \times$ ULN
 - b) Total bilirubin > 2 times the upper limit of normal
 - c) ALP $< 2 \times$ ULN
 - d) There is no explanation for the above laboratory abnormalities a), b), and c) other than investigational product.
- (3) Neurological disorders (medically significant changes on neurological examination in the healthy side)

If such an adverse event occurs, the investigator must inform the monitor immediately about the situation. The monitor will confirm with the investigator (subinvestigator) whether or not the study can be continued.

For significant adverse events, the sponsor will appropriately evaluate the occurrence status and frequency, and examine the appropriateness of study continuation and the necessity of protocol amendment.

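### The reflex score merges increased with normal, so the scored neurotoxicity examination cannot show new hyperreflexia and may display it as improvement

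*Protocol*

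**What the plan says.** Protocol 5.4.2 explains why the examination exists: "delayed neurotoxicity was observed in nonclinical studies of this drug", so it was added to the general safety endpoints to "check for the development of symptoms due to neuropathy of peripheral nerves and notochord".

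Under Protocol 9.2.4.1 (4) the investigator "will perform a neurological examination on the healthy side once from the onset to Day5", and again on Day 14, at Week 3, at discharge and at 3 months. The reflexes are "Biceps brachii reflex, triceps brachii reflex, patellar tendon reflex, Achilles tendon reflex". Each is scored "0: No abnormality or increased", 1 for decreased, or "2: Elimination". For the examination as a whole, "the date and results will be recorded in the CRF". No separate field for an increased reflex is described. The five sensory items also grade only weakening or loss.

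Protocol 11.2 lists three kinds of significant adverse event. The third is "Neurological disorders (medically significant changes on neurological examination in the healthy side". Protocol 13.3.3 plans shift tables of the neurological examination by group and time point. SAP 7.3.6 plans only a listing (16.2.7.1), and the table list in SAP 14.2 contains no neurological table. SAP section 8, on changes from the protocol, does not mention the omission.

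**The concern.** The stated purpose names two sites: peripheral nerves and a second one rendered as notochord. If that word stands for the spinal cord, the examination has a central target as well as a peripheral one. As a matter of general neurology, a central lesion can make reflexes brisker, whereas a peripheral neuropathy tends to reduce them. A scale that runs only from normal to absent can register the second direction and not the first.

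At stake is how the results are read. An examination added to look for a specific toxicity could return code 0 throughout, and a reader could take that as evidence that reflexes were normal in every arm. The scored record would not support that reading. The examiner has already elicited the reflex, so the coding discards information that cost nothing extra to obtain.

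**Working it through.** No sample size, power or significance level is involved, and the plan states no figure to reproduce. The check maps reflex states to codes and asks which changes remain visible.

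**Inputs** (Protocol 9.2.4.1 (4)). There are four possible states: normal, increased, decreased, absent. They map to three codes: normal = 0, increased = 0, decreased = 1, absent = 2.

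**Step 1: pairs and cells.** Two examinations give 4 × 4 = 16 possible pairs of states. Three codes give 3 × 3 = 9 shift-table cells. The cell 0 to 0 alone holds 2 × 2 = 4 pairs: normal to normal, normal to increased, increased to normal, and increased to increased.

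**Step 2: changes to a newly increased reflex.** There are three.

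| First examination | Later examination | Codes recorded | Reads as |
|---|---|---|---|
| normal | increased | 0 to 0 | no change |
| decreased | increased | 1 to 0 | improvement |
| absent | increased | 2 to 0 | improvement |

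Each shares its cell with a different event: stable normal, recovery from decreased, and recovery from absent. The score identifies 0 of 3. This holds for each of the four reflexes at every visit. It applies equally to a listing, if the listing shows the codes alone.

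**Step 3: routes that do not use the score.** Protocol 9.2.4.2 defines adverse events to include unfavourable or unintended signs. It treats any objective finding that the investigator considers clinically significant as an adverse event, to be entered in the CRF. Protocol 11.2 (3) rests on medical significance, not on a change of code, and requires immediate contact with the monitor. Adverse events are tabulated by system organ class and preferred term (Protocol 13.3.3, SAP 7.3.1). A brisk reflex judged significant can therefore reach the data. What is lost is systematic capture, above all of increases that the investigator does not judge significant.

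**Step 4: whether the first examination is a baseline.** Protocol 9.2.4.1 allows it up to Day 5, and the footnote in SAP Appendix 1 treats an examination in that window as the baseline. The continuous infusion starts on Day 1 and lasts 72 hours, so it ends around Day 4. An examination on Day 5 follows it. The first examination is thus not guaranteed to precede dosing and cannot by itself separate stroke-related or earlier hyperreflexia from a change on treatment.

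**The case against.** The best defence is that the scale is a deliberate loss-of-function screen. The wording of code 0 is explicit, the sensory items also grade only loss, and such an instrument suits a search for peripheral neuropathy. This stands for the peripheral part of the purpose. It does not explain why an abnormal sign should share a code with normal when the second stated site may be central.

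A reader might infer more than the documents support, in four ways.

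- **That hyperreflexia can never appear in the data.** It can, through the adverse event rules in Protocol 9.2.4.2 and 11.2. That route depends on individual judgement. The ECG and vital-sign items in 9.2.4.1 repeat the instruction to report significant findings as adverse events, and the neurological item does not, but the general rule still covers it.
- **That the trial's shift tables will be biased.** The current SAP plans none for this examination. The blind spot passes to the listing instead.
- **That the drug is known to cause a cord lesion with brisk reflexes.** The public text gives no nonclinical detail on lesion site or reflex direction, and reading notochord as spinal cord is a guess at a translation.
- **That the merged code can never be separated.** Source records may describe the reflex, and the CRF is not available to us, so a comment field cannot be excluded.

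It is also fair to say that recruitment has stopped and results are described as exploratory (SAP section 1), so a new code has limited prospective value in this trial.

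**Conclusion.** The point holds in a limited form. The reflex score cannot show new hyperreflexia: 0 of 3 possible changes are identifiable, and two of the three would be displayed as improvement. The sign is captured only when the investigator judges it significant and reports it as an adverse event.

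The coding gap itself needs no assumption, as it follows from the printed scale. Its importance depends on notochord meaning spinal cord, and on how often reflexes increase on the healthy side, which the documents do not say. That the listing shares the gap assumes that it shows the coded score without comment text. The point is minor: no efficacy result is touched, and the remaining consequence is that code 0 could be mistaken for a normal finding.

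**What to change.** - **Scale and CRF.** In Protocol 9.2.4.1 (4) and the CRF, give increased reflexes their own code, for example 0 normal, 1 decreased, 2 absent, 3 increased. This serves any data still to be collected and any later study that uses the scale.
- **SAP.** Show increased as its own category by arm in listing 16.2.7.1. Restore the neurological shift table planned in Protocol 13.3.3 with the same category, or record its omission in SAP section 8. A version pooled with normal can be kept as a sensitivity table.
- **Data already collected.** Query source records behind code 0 where feasible. Review adverse events by arm for healthy-side hyperreflexia. State in the SAP and the clinical study report that code 0 includes increased reflexes and must not be read as normal.

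The cost is one code, one table category, a sentence of explanation and a targeted review, with no extra examination. The downside is that some increased reflexes will reflect the stroke or earlier disease. Because the first examination may be as late as Day 5, the main safeguard is the randomised comparison between arms, at whatever precision the reduced sample allows.
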